## 11.7 Publication Policy

Following completion of the study, the data may be considered for publication in a scientific journal or for reporting at a scientific meeting. Each Investigator is obligated to keep data pertaining to the study confidential. The Investigator must consult with the Sponsor before any study data are submitted for publication. The Sponsor reserves the right to deny publication rights until mutual agreement on the content, format, interpretation of data in the manuscript, and journal selected for publication are achieved.

# 11.8 Financial Disclosure

Investigators are required to provide financial disclosure information to the Sponsor to permit the Sponsor to fulfill its obligations under 21 CFR Part 54. In addition, Investigators must commit to promptly updating this information if any relevant changes occur during the study and for a period of 1 year after the completion of the study.

## 12 STUDY ADMINISTRATIVE INFORMATION

## 12.1 Protocol Amendments

Any amendments to the study protocol will be communicated to the Investigators by Medpace or the Sponsor. All protocol amendments will undergo the same review and approval process as the original protocol. A protocol amendment may be implemented after it has been approved by the IRB, unless immediate implementation of the change is necessary for patient safety. In this case, the situation must be documented and reported to the IRB within 5 working days.

# **APPENDIX A: SCHEDULE OF PROCEDURES**

	Screeninga	Treatment Period							Safety Follow-up b		
	Visit 1	Visit 2	Visit 3	Visit 4	Visit 5	Visit 6	Visit 7	Visit 8	Visit 9	Visit 10	ET
Study Week	-8 to -1	0	4	10	16	24	32	40	52	54	Visit b
Study Day	-56 to -1	0	28	70	112	168	224	280	364	378	
Visit Window		±0 days	±5 days	±7 days	±5 days						
Assessment											
Informed consent	X										
Eligibility criteria	X	Xc									
Demographics	X										
Medical history	X	X									
Prior/concomitant medications d	X	X	X	X	X	X	X	X	X	X	X
Height and body weight e	X	X	X	X	X	X	X	X	X	X	X
BMI calculation	X	X									
Physical examination f	X	X	X	X	X	X	X	X	X	X	X
Vital signs g	X	X	X	X	X	X	X	X	X	X	X
AUDIT-C h	X										
Viral serology i	X										
Fasting hematology,											
biochemistry, coagulation, and											
lipid panels j	X	X	X	X	X	X	X	X	X	X	X
Lipoprotein particle size		X			X				X		X
Urinalysis k	X	X	X	X	X	X	X	X	X	X	X
Pregnancy test 	X	X	X	X	X	X	X	X	X	X	X
12-lead ECG m	X	X			X		X		X	X	X
FibroScan ®	X n										
MRI-PDFF and cT1 imaging o	X	Xp			X				X		X
Liver biopsy	X q								X r,s		$X^b$
Randomization		X									
Adverse event monitoring	X	X	X	X	X	X	X	X	X	X	X
Biomarker sampling t		X			X				X		X
PK sampling u		X v	X	X	X	X	X	X	X		X

Lipidomic analyses sampling w	X							X	X
Study drug administration/									
dispensing r,x	X	X	X	X	X	X	X		
Study drug accountability y	•	X	X	X	X	X	X	X	X

COVID-19 contingency measures: This study protocol includes contingency measures to manage disruptions due to COVID-19 control measures, including modifications to visit schedules and procedures specific to situations where COVID-19 is impacting study conduct. See Appendix G for details of COVID-19 contingency measures. In the absence of a COVID-19 impact, it is expected that Investigators and patients follow the protocol requirements as set forth.

- a. The screening period of up to 8 weeks may include more than 1 visit. Patients who screen fail may be rescreened once.
- b. Patients who discontinue early from the study for any reason prior to completion of the treatment period will be requested to return to the clinic for an ET Visit as soon as possible after their last intake of study drug. Liver biopsy at ET will be only performed for patients who have been on study drug for at least 6 months. If a patient discontinues early from the study for any reason after completion of the treatment period but before the Safety Follow-up Visit, sites should make every attempt to bring the patient into the site for the Safety Follow-up Visit.
- c. Eligibility criteria will be reassessed prior to dosing with study drug to ensure no changes in eligibility have occurred since screening.
- d. All prior and concomitant medications will be documented in the eCRF. Prior medications include any medication taken within 6 months prior to screening. Concomitant medications include any medication taken on or after the date the patient signs informed consent. Unless medically warranted, all concomitant medications should remain stable from screening through the Safety Follow-up Visit (Visit 10). Throughout the duration of the study, patients should not introduce changes to their usual diet (including dietary supplements) or lifestyle. Any changes to concomitant medication dosing during the study will be captured in the eCRF and closely monitored.
- e. Height will be measured at screening only. Body weight will be measured at every visit.
- f. Full physical examinations (including general appearance; eyes, ears, nose, and throat; head and neck; chest and lungs; cardiovascular; abdomen; musculoskeletal; lymphatic; dermatological; neurological systems; mental status; and extremities) will be performed at screening; Visits 2 and 9; and at study exit (whether at the Safety Follow-up or ET Visit). Abbreviated physical examinations will be performed at all other visits.
- g. Vital signs will include blood pressure, pulse rate, and body temperature, and will be performed with the patient in the sitting position after 5 minutes of rest and before any blood draws. Three replicate blood pressure readings will be taken at each visit.
- h. Only patients with AUDIT-C scores ≥3 points at screening will receive the full AUDIT at screening and will be excluded if they score ≥8 points on the full AUDIT. Patients with AUDIT-C scores <3 points will not receive the full AUDIT.
- i. Patients must test negative for hepatitis B virus, HCV (patients with a confirmed history of HCV infection can be included if HCV PCR is negative for at least the last 2 years), and HIV infection to be eligible for the study.
- j. If a patient has a qualifying historical biopsy, the required AST levels (AST ≥20 U/L in men and ≥17 U/L in women by central laboratory or AST ≥30 U/L by a local laboratory within 60 days of screening) will not apply.
- k. Further analysis of urine sediment or urine microscopy will be performed if there are any abnormalities on any of the following 3 dipstick results: leukocyte esterase, blood, or nitrite.
- For women of childbearing potential, a serum hCG pregnancy test will be performed at screening, Week 0, and at study exit (whether at the Safety Follow-up or ET Visit).
   Urine hCG testing will be performed at all other visits. If a urine hCG test is positive, pregnancy will be confirmed by a serum hCG test. Follicle-stimulating hormone level will be measured at screening to confirm postmenopausal state in women ≤55 years of age.
- m. Single 12-lead ECGs will be performed after the patient has been resting in the supine position for at least 10 minutes. In case of evident bad quality of the tracing (eg, muscle tremor), the ECG will be repeated. QTcF will be measured.
- n. Patients without a historical biopsy must have a FibroScan® VCTE measurement ≥8.5 kPa and a CAP for steatosis with cut-off values ≥300 dB/m at screening or a historical FibroScan (with eligible VCTE and CAP values) within 90 days of screening. FibroScan is not required for patients who have evaluable histology slides from a liver biopsy performed in the previous 6 months available for review by the central pathology reader.
- o. At screening, perform MRI-PDFF if FibroScan values (VCTE and CAP) are within eligibility range (for patients without historical biopsy) or if the patient has a qualifying historical biopsy. If the patient is eligible based on a historical biopsy, the MRI-PDFF procedure should be performed but the eligibility criterion of liver fat content ≥8% will not be applied. Magnetic resonance imaging-PDFF will be performed using a standardized central imaging protocol and will be validated by the central imaging reader at screening (as the baseline value), Visit 5 (Week 16), and Visit 9 (Week 52) or the ET Visit. Iron-corrected T1 will be calculated for all randomized patients at Visit 2 (Week 0) (using the screening MRI), Visit 5 (Week 16), and Visit 9 (Week 52) or the ET Visit.

- p. At Visit 2, cT1 will be calculated from the screening MRI only if the patient is randomized. No MRI will be performed at Visit 2.
- q. Historical liver biopsy within 6 months of screening may be used for eligibility if evaluable histology slides are available for review by the central pathology reader. Patients must not have received nonalcoholic steatohepatitis therapy since the historical biopsy was obtained. Historical liver biopsies obtained during the course of a prior investigational drug study must not be utilized if obtained within 3 months or 5 half-lives of the last dose of the prior investigational drug, whichever is longer.
- r. In the event that the Visit 9 biopsy is delayed, patients will continue to administer study drug daily until the biopsy occurs for up to 30 days after the originally projected Visit 9 date.
- s. In a subgroup of patients, biopsy tissue collected at the End of Treatment/Visit 9 will be used to perform lipidomic analyses.
- t. Biomarkers to be assessed include: HOMA-IR, hsCRP, Pro-C3, and ELF panel.
- u. Pharmacokinetic sampling will occur at Visits 2 to 9 at time 0 (predose, ie, within 1 hour prior to the first dose).
- v. For those patients participating in the intensive PK subset, PK blood samples will be collected in relation to the first dose of study drug at Visit 2. Samples will be taken at the following timepoints: predose (within 1 hour prior to the first dose), followed by 1, 2, 3, 4, 6, and 8 hours postdose (±10 minutes) at Visit 2 (Day 0) and 24 hours postdose (±1 hour, but prior to the second dose of study drug on Day 1).
- w. In a subgroup of patients, fasting serum samples will be collected to perform lipidomic analyses.
- x. On Visits 2 to 8, study drug will be administered to the patient on site to accommodate trough PK sampling prior to dosing. Sufficient study drug will be dispensed to the patient for dosing until the next study visit.
- y. Returned and used/unused study drug will be collected to assess compliance.

AUDIT = Alcohol Use Disorders Identification Test; AUDIT-C = Alcohol Use Disorders Identification Test-Concise; BMI = body mass index; CAP = controlled attenuation parameter; COVID-19 = Coronavirus Disease 2019; cT1 = iron-corrected T1; ECG = electrocardiogram; eCRF = electronic case report form; ELF = enhanced liver fibrosis; ET = Early Termination; hCG = human chorionic gonadotropin; HCV = hepatitis C virus; HIV = human immunodeficiency virus; HOMA-IR = Homeostatic Model Assessment for Insulin Resistance; hsCRP = high-sensitivity C-reactive protein; MRI-PDFF = magnetic resonance imaging-proton density-fat fraction; PCR = polymerase chain reaction; PK = pharmacokinetics; VCTE = vibration-controlled transient elastography.

## APPENDIX B: CLINICAL LABORATORY ANALYTES

**Biochemistry Panel** 

Alanine aminotransferase Albumin
Alkaline phosphatase Amylase
Aspartate aminotransferase Bicarbonate
Blood urea nitrogen Calcium

Chloride Creatine kinase

Creatinine Estimated glomerular filtration rate

Gamma glutamyl transferase Glucose

Inorganic phosphorus Lactate dehydrogenase

Lipase Potassium

Sodium Total bilirubin [1]

Total protein Uric acid

1. If total bilirubin is above the upper limit of normal, add conjugated (direct) bilirubin.

# Hematology

range.

Hematocrit Hemoglobin
Neutrophils Platelets

Red blood cell count and differential [1]

1. Manual microscopic review is performed only if white blood cell count and/or differential values are out of reference

## **Lipid and Metabolic Profile**

Apolipoprotein B Apolipoprotein C3

Hemoglobin A1c High-density lipoprotein-cholesterol

Lipoprotein(a) Lipoprotein particle size [1]

Low-density lipoprotein-cholesterol Remnant cholesterol

Serum cholesterol Triglycerides

 Lipoprotein particle size will be assessed only at baseline, Week 16, and at the end of treatment (Week 52/Early Termination).

# Plasma/Serum and Liver Lipidomics

Acyl carnitines Acyl-ether-phospholipids

Amino acids Bile acids

Cholesteryl esters Diacyl-phospholipids

Fatty acids Glycerolipids

Icosabutate and icosabutate metabolites Lyso-phospholipids N-acyl ethanolamines Oxidized fatty acids

Primary fatty acid amides Sphingolipids

# Coagulation

Activated partial thromboplastin time Fibrinogen

International normalized ratio Prothrombin time

## **Liver Inflammation and Fibrosis Biomarkers**

Enhanced liver fibrosis panel High-sensitivity C-reactive protein

Homeostatic Model Assessment for Insulin Pro-C3

Resistance

# Endocrinology

Human chorionic gonadotropin (hCG) [1] Follicle-stimulating hormone (FSH) [2] Thyroid-stimulating hormone (TSH) [3]

- 1. For women of childbearing potential, a serum hCG pregnancy test will be performed at screening, Week 0, and at study exit (whether at the Safety Follow-up Visit or Early Termination Visit). Urine hCG testing will be performed at all other visits. If a urine hCG test is positive, pregnancy will be confirmed by a serum hCG test.
- 2. FSH level will be measured at screening to confirm postmenopausal state in women ≤55 years of age.
- 3. Free triiodothyronine and free thyroxine will be measured if TSH is abnormal.

# Urinalysis [1]

Bilirubin Blood
Glucose Ketones
Leukocyte esterase Microscopy

Nitrite pH

Protein Specific gravity

Urobilinogen

1. Dipstick urine qualitatively. Further analysis of urine sediment or urine microscopy will be performed if there are any abnormalities on any of the following 3 dipstick results: leukocyte esterase, blood, or nitrite.

## Serology

Hepatitis B surface antigen Hepatitis C virus antibody (and polymerase

chain reaction ribonucleic acid for positive

antibody samples)

Human immunodeficiency virus

# APPENDIX C: ALCOHOL USE DISORDERS IDENTIFICATION TEST-CONCISE

The Alcohol Use Disorders Identification Test-Concise (AUDIT-C) has 3 questions and is scored on a scale of 0 to 12. Read the questions as written and circle the letter that corresponds to the answer. Each AUDIT-C question has 5 answer choices valued from 0 to 4 points. In men, a score of 4 or more is considered positive, optimal for identifying hazardous drinking or active alcohol use disorders. In women, a score of 3 or more is considered positive. Generally, the higher the score, the more likely it is that a person's drinking is affecting his or her safety.

AUDII	1-C Questionnaire	
Patient	t ID	Visit date
1.	How often do you have a drink coa. Never b. Monthly or less c. 2-4 times a month d. 2-3 times a week e. 4 or more times a week	ontaining alcohol?
2.	How many standard drinks conta a. 1 or 2 b. 3 or 4 c. 5 or 6 d. 7 to 9 e. 10 or more	ining alcohol do you have on a typical day?
3.	How often do you have six or mo a. Never b. Less than monthly c. Monthly d. Weekly e. Daily or almost daily	re drinks on one occasion?

See answer module on the next page.

# **Answer Module**

# Question 1: How often do you have a drink containing alcohol?

## Valid Values

Value	Value Meaning	Description	Display Order
Never	Never	Not ever; at no time in the past (or future).	0
Monthly or less	Monthly or less	Monthly or less	
2 to 4 times a month	Two To Four Instance Per Month	a function word to indicate direction, purpose, or movement.: A natural number greater than 3 and less than 5 and the quantity that it denotes: the sum of three and one.: An occurrence of something.: For each, generally denoting a ratio.: One of the 12 divisions of a year as determined by a calendar. It corresponds to the unit of time of	
2 to 3 times a week	Two To Three Instance Per Week		
4 or more times a week	Than Integer::4 the same thing; used in correlation; used to correct or rephrase what was previously said; otherwise.: A statemen about the relative size or order of two objects specifying that an object of interest exceeds another object in		4

# Question 2: How many standard drinks containing alcohol do you have on a typical day?

## **Valid Values**

Value	Value Meaning	Description	Display Order
1 or 2	1 or 2	1 or 2	0
3 to 4	3 to 4	3 to 4	1
5 to 6	5 to 6	5 to 6	2
7 to 9	7 to 9	7 to 9	3
10 or more	10 or more	10 or more	4

# Question 3: How often do you have six or more drinks on one occasion?

## **Valid Values**

THE THINKS			
Value	Value Meaning	Description	Display Order
Never	Never	Not ever; at no time in the past (or future).	0
Less than monthly	Less Than Monthly	A statement about the relative size or order of two objects specifying that an object of interest is smaller than another object in quantity or measure or value or status.: Every month.	
Monthly	Monthly	Every month.	2
Weekly	Weekly	Every week.	3
Daily or			
almost daily	Daily	Occurring or done each day.	4

# APPENDIX D: ALCOHOL USE DISORDERS IDENTIFICATION TEST: INTERVIEW VERSION

Read questions as written. Read answers carefully. Begin the AUDIT by saying "Now I am going to ask you some questions about your use of alcoholic beverages during this past year." Explain what is meant by "alcoholic beverages" by using local examples of beer, wine, vodka, etc. Code answers in terms of "standard drinks." Place the correct answer number in the box at the right. Total scores of ≥8 are recommended as indicators of hazardous and harmful alcohol use.

1. How often do you have a drink containing alcohol?  (0) Never [Skip to Qs 9-10] (1) Monthly or less (2) 2 to 4 times a month (3) 2 to 3 times a week (4) 4 or more times a week	6. How often during the last year have you needed a first drink in the morning to get yourself going after a heavy drinking session?  (0) Never (1) Less than monthly (2) Monthly (3) Weekly (4) Daily or almost daily
2. How many drinks containing alcohol do you have on a typical day when you are drinking?  (0) 1 or 2 (1) 3 or 4 (2) 5 or 6 (3) 7, 8, or 9 (4) 10 or more	7. How often during the last year have you had a feeling of guilt or remorse after drinking?  (0) Never  (1) Less than monthly  (2) Monthly  (3) Weekly  (4) Daily or almost daily
3. How often do you have six or more drinks on one occasion?  (0) Never (1) Less than monthly (2) Monthly (3) Weekly (4) Daily or almost daily  Skip to Questions 9 and 10 if Total Score for Questions 2 and 3 = 0	8. How often during the last year have you been unable to remember what happened the night before because you had been drinking?  (0) Never (1) Less than monthly (2) Monthly (3) Weekly (4) Daily or almost daily
4. How often during the last year have you found that you were not able to stop drinking once you had started?  (0) Never (1) Less than monthly (2) Monthly (3) Weekly (4) Daily or almost daily	9. Have you or someone else been injured as a result of your drinking?  (0) No (2) Yes, but not in the last year (4) Yes, during the last year
5. How often during the last year have you failed to do what was normally expected from you because of drinking?  (0) Never (1) Less than monthly (2) Monthly (3) Weekly (4) Daily or almost daily	10. Has a relative or friend or a doctor or another health worker been concerned about your drinking or suggested you cut down?  (0) No (2) Yes, but not in the last year (4) Yes, during the last year

# APPENDIX E: DRUG-INDUCED LIVER INJURY MONITORING PLAN

Throughout the study, all treatment-emergent adverse events, clinical assessments, and clinical laboratory parameters will be closely monitored against the criteria for suspected drug-induced liver injury as detailed in this Monitoring Plan.

Patients with normal liver transaminases and bilirubin at baseline

# Patients With Normal Liver Transaminases and Bilirubin at Baseline

Elevations in AST or ALT >2  $\times$  ULN or TBL >1.5  $\times$  ULN values during the study

Perform repeat testing within 48 hours.

If persistent elevations upon repeat testing, implement close observation to seek other possible causes of the observed liver test abnormalities. Discontinuation of study drug should be considered.

## Discontinue study drug if:

- ALT or AST >8 × ULN
- ALT or AST >5 × ULN for >2 weeks
- ALT or AST >3 × ULN and TBL >2 × ULN or INR >1.5
- ALT or AST >3 × ULN with the appearance of fatigue, nausea, vomiting, right upper quadrant pain or tenderness, fever, rash, and/or eosinophilia (>5%)

AND follow the patient until resolution of signs/symptoms.

ALT = alanine aminotransferase; AST = aspartate aminotransferase; INR = international normalized ratio; TBL = total bilirubin; ULN = upper limit of normal.

Suspected drug-induced liver injury monitoring in patients with normal liver transaminases and bilirubin at baseline should be performed throughout the study according to the procedures summarized below.

- If patients with normal baseline liver indices develop elevations of aspartate aminotransferase (AST) or alanine aminotransferase (ALT) >2 × upper limit of normal (ULN) or total bilirubin (TBL) >1.5 × ULN values during the study, repeat testing should be performed within 48 hours.
  - o If there are persistent elevations (ALT or AST >2 × ULN or TBL >1.5 × ULN) upon repeat testing, close observation (testing and physical examination 2 to 3 times per week) should be implemented. An important purpose of the close observation is to gather additional clinical information to seek other possible causes of the observed liver test abnormalities, such as one of the following: acute viral hepatitis, alcoholic and autoimmune hepatitis, hepatobiliary disorders, cardiovascular causes, or concomitant treatments. Discontinuation of study drug should be considered.
- Study drug should be discontinued, and the patient should be followed until resolution of signs or symptoms, in the following situations:
  - $\circ$  ALT or AST >8 × ULN.
  - $\circ$  ALT or AST >5 × ULN for more than 2 weeks.
  - $\circ$  ALT or AST > 3 × ULN and (TBL > 2 × ULN or international normalized ratio [INR] > 1.5).
  - $\circ$  ALT or AST >3 × ULN with the appearance of fatigue, nausea, vomiting, right upper quadrant pain or tenderness, fever, rash, and/or eosinophilia (>5%).

For any patients who present with a constellation of syndromes indicative of liver disease as per the Investigator's overall assessment (ie, fatigue, nausea, vomiting, right upper quadrant pain or tenderness, fever, rash, and/or eosinophilia [>5%]), perform liver function tests to determine if liver disease is worsening and discontinue the study drug if worsening is confirmed.

Reinitiation of study drug may be considered after consultation with the Medical Monitor.

## Patients with elevations in liver transaminases or bilirubin at baseline

# Patients With Elevations in Liver Transaminases or Bilirubin at Baseline

New elevations in AST or ALT >2  $\times$  baseline average or TBL >1.5  $\times$  baseline average values during the study

Perform repeat testing within 48 hours.

If persistent elevations upon repeat testing, implement close observation to seek other possible causes of the observed liver test abnormalities. Discontinuation of study drug should be considered.

# Discontinue study drug if:

- Baseline average measurements were <2 × ULN and ALT or AST increases to >5 × baseline measurements
- Baseline average measurements were ≥2 × ULN (but <5 × ULN) and ALT or AST increases to >3 × baseline measurements
- Baseline average measurements were ≥5 × ULN and ALT or AST increases to >2 × baseline measurements
- ALT or AST increase >2 × baseline average measurements AND the increase is accompanied by a concomitant increase in TBL to >2 × baseline average measurements or the INR concomitantly increases by >0.2

AND follow the patient until resolution of signs/symptoms.

ALT = alanine aminotransferase; AST = aspartate aminotransferase; INR = international normalized ratio; TBL = total bilirubin; ULN = upper limit of normal.

Suspected drug-induced liver injury monitoring in patients with elevations in liver transaminases or bilirubin at baseline should be performed throughout the study according to the procedures summarized below.

- If patients with abnormal baseline liver indices develop elevations of AST or ALT >2 × baseline average or TBL >1.5 × baseline average values during the study, repeat testing should be performed within 48 hours.
  - o If there are persistent elevations (ALT or AST >2 × baseline average or TBL >1.5 × baseline average values) upon repeat testing, then close observation (testing and physical examination 2 to 3 times per week) should be implemented and discontinuation of study drug should be considered.
- Discontinue the study drug if any of the following occur:
  - o Baseline average measurements were  $<2 \times ULN$  and ALT or AST increases to  $>5 \times baseline$  measurements.
  - O Baseline average measurements were  $\geq 2 \times \text{ULN}$  (but  $< 5 \times \text{ULN}$  as per eligibility requirements) and ALT or AST increases to  $> 3 \times \text{baseline}$  measurements.
  - o Baseline average measurements were  $\geq 5 \times \text{ULN}$  and ALT or AST increases to  $\geq 2 \times \text{baseline}$  measurements.
  - o ALT or AST increase >2 × baseline average measurements AND the increase is accompanied by a concomitant increase in TBL to >2 × baseline average measurements or the INR concomitantly increases by >0.2.

For any patients who present with a constellation of syndromes indicative of liver disease as per the Investigator's overall assessment (ie, fatigue, nausea, vomiting, right upper quadrant pain or tenderness, fever, rash, and/or eosinophilia [>5%]), perform liver function tests to determine if liver disease is worsening and discontinue the study drug if worsening is confirmed.

Reinitiation of study drug may be considered after consultation with the Medical Monitor.

For all patients, close observation for suspected drug-induced liver injury includes the following:

- Repeating liver enzyme (ALT, AST, and alkaline phosphatase) and serum bilirubin tests 2 or 3 times weekly (if a patient lives in a remote area, he or she can be tested locally and the results promptly communicated to the study site).
- The frequency of repeat testing can decrease to once a week or less if abnormalities stabilize or the study drug has been discontinued and the patient is asymptomatic.
- Obtaining a more detailed history of symptoms and prior or concurrent diseases.
- Obtaining a history of concomitant drug use (including nonprescription medications and herbal and dietary supplement preparations), alcohol use, recreational drug use, and special diets.
- Ruling out acute viral hepatitis types A, B, C, D, and E; autoimmune or alcoholic hepatitis; hypoxic/ischemic hepatopathy; and biliary tract disease.
- Obtaining a history of exposure to environmental chemical agents.
- Obtaining additional tests to evaluate liver function, as appropriate (eg, INR, direct bilirubin).
- Considering gastroenterology or hepatology consultations.

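### Appendix E sets no × ULN ceiling or time limit for raised-baseline patients, so those entering at 1.6 to <2.0 × ULN can reach 8 to just under 10 × ULN before an enzyme-only stop

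*Protocol*

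**What the plan says.** Protocol Appendix E has separate rules for patients with normal and with raised liver tests at baseline.

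**Normal baseline.** Study drug must stop if ALT or AST exceeds 8 × ULN, exceeds 5 × ULN for more than two weeks, or exceeds 3 × ULN together with a bilirubin or INR criterion or with symptoms.

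**Raised baseline.** There are three enzyme-only stops, each tied to a baseline tier:

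- The lowest tier has the largest multiple: "Baseline average measurements were <2 × ULN and ALT or AST increases to >5 × baseline measurements"
- The middle tier covers the rest of the range allowed at entry: "Baseline average measurements were ≥2 × ULN (but <5 × ULN) and ALT or AST increases to >3 × baseline measurements"
- The highest tier has the smallest multiple: "Baseline average measurements were ≥5 × ULN and ALT or AST increases to >2 × baseline measurements"

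A fourth stop applies when ALT or AST exceeds 2 × baseline and either bilirubin exceeds 2 × baseline or INR rises by more than 0.2. For patients with symptoms that suggest liver disease, liver tests are done and the instruction is to "discontinue the study drug if worsening is confirmed".

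Below these limits, a new rise above 2 × baseline leads to "Perform repeat testing within 48 hours". If it persists, "close observation (testing and physical examination 2 to 3 times per week) should be implemented and discontinuation of study drug should be considered". Appendix E then adds: "The frequency of repeat testing can decrease to once a week or less if abnormalities stabilize".

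Elsewhere in the protocol, Inclusion Criterion 7 (Section 4.1) requires ALT and AST below 5 × ULN at entry. Section 4.3 lists a severe laboratory abnormality as a reason why participation may end and points back to Appendix E. Section 8.1.4 makes suspected drug-induced liver injury an adverse event of special interest, submitted within 24 hours. Section 9.2.4 provides for independent review of unblinded safety data. The SAP contains no stopping rule.

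**The concern.** The protocol treats an absolute level (8 × ULN) and a duration (5 × ULN for more than two weeks) as mandatory stops when baseline is normal. Neither is carried over to patients with raised baselines. For an isolated rise, with no symptoms and no bilirubin or INR change, only the baseline multiple then forces a stop.

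Two oddities follow in the lowest tier. A patient who entered just under 2 × ULN may reach a higher level than either a normal-baseline patient or one who entered at exactly 2 × ULN. And a stable plateau above 5 × ULN but below 5 × baseline never requires a stop, however long it lasts; once it is stable, testing may even become less frequent. This is the liver stopping rule in a liver-disease population, so the inconsistency deserves correction. What is at stake is patient safety in a narrow setting.

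**Working it through.** The plan states no × ULN limit for raised-baseline patients, so there is no figure of its own to reproduce. The inputs are the Appendix E multiples, the two normal-baseline limits, and the entry limit of 5 × ULN.

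Let b be baseline ALT or AST in × ULN, with b above 1. The level above which an enzyme-only stop is mandatory is:

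- L(b) = 5b for b < 2
- L(b) = 3b for 2 ≤ b < 5
- L(b) = 2b for b ≥ 5

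**Where L exceeds 8 × ULN.** In the first tier, b > 8/5 = 1.6. In the second, b > 8/3 = 2.67. At baselines of 1 to 1.6 and 2 to 2.67 the limit is already at or below 8 × ULN.

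**Step at b = 2.** 5 × 1.99 = 9.95, but 3 × 2.0 = 6.0. The limit falls by 3.95 × ULN for a difference of 0.01 × ULN in baseline.

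**Duration.** For every b between 1 and 2, 5b exceeds 5, so the range from 5 to 5b × ULN has no time limit: 5 to 5.5 at b = 1.1, 5 to 7.5 at b = 1.5, 5 to 9.95 at b = 1.99. For example, at 9 × ULN for three weeks a normal-baseline patient must stop. One who entered at 1.9 × ULN has risen 9/1.9 = 4.7-fold and need not.

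**Effect of a ceiling.** The table uses min(5b, 8) for b < 2 (recommended) and min(3b, 10) for 2 ≤ b < 5 (optional).

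| Baseline (× ULN) | Stop now (× ULN) | Recommended ceiling | With optional ceiling | Fold rise at lowest limit |
|---|---|---|---|---|
| 1.1 | 5.5 | 5.5 | 5.5 | 5.0 |
| 1.6 | 8.0 | 8.0 | 8.0 | 5.0 |
| 1.9 | 9.5 | 8.0 | 8.0 | 4.2 |
| 1.99 | 9.95 | 8.0 | 8.0 | 4.02 |
| 2.0 | 6.0 | 6.0 | 6.0 | 3.0 |
| 2.67 | 8.0 | 8.0 | 8.0 | 3.0 |
| 4.0 | 12.0 | 12.0 | 10.0 | 2.5 |
| 4.9 | 14.7 | 14.7 | 10.0 | 2.04 |
| 4.99 | 14.97 | 14.97 | 10.0 | 2.00 |

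The recommended ceiling binds only for 1.6 < b < 2.0 and still requires at least a 4-fold rise. It cuts the step at b = 2 from 3.95 to 8 − 6 = 2.0 × ULN. The duration rule acts at 5/1.99 = 2.51-fold or more, above the 2 × baseline trigger for repeat testing.

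The optional ceiling binds for b > 10/3 = 3.33. Near b = 5 it almost coincides with the repeat-test trigger: at b = 4.99 the trigger is 2 × 4.99 = 9.98 and the ceiling is 10.0.

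**The case against.** The best defence is that scaling stops to baseline is a deliberate and sensible choice when enzymes start high, and that × ULN limits belong to patients who start normal. In fold terms the raised-baseline rule is the stricter one: it stops at 5-fold or 3-fold, whereas a normal-baseline patient above 8 × ULN has risen at least 8-fold. This stands. A reader might infer that raised-baseline patients are held to a looser rule overall, and the documents do not support that. The point concerns only the absolute level reached and the time spent there, and for baselines of 1 to 1.6 and 2 to 2.67 × ULN the level is no higher than 8 × ULN.

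A reader might also make much of the fall from just under 15 to 10 × ULN at baseline 5. That boundary is largely theoretical, because entry requires less than 5 × ULN. It could be crossed only if the baseline average, which Appendix E does not define, included a higher sample taken before entry.

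Nor are these patients unwatched. The 48-hour repeat, close observation with a work-up for other causes, 24-hour special-interest reporting, committee review, and the symptom and bilirubin/INR stops all apply. None of them, however, requires a stop for an isolated, symptom-free rise.

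Finally, the Week 16 interim results in Section 1.4.1 are reassuring. Placebo-adjusted ALT fell by 19 and 25.4 U/L, AST fell by 9.4 and 13.5 U/L, and there was no confirmed drug-induced liver injury. That suggests the rule will seldom be tested, which limits the size of the point but does not explain the step at baseline 2.

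**Conclusion.** The gap is real but minor. For an isolated, symptom-free rise without a bilirubin or INR change, patients who entered at 1.6 to under 2.0 × ULN may reach 8 to just under 10 × ULN before a mandatory stop. The limit is 8 × ULN for normal-baseline patients and 6 × ULN for those who entered at 2.0. In the tier from 2 to under 5 × ULN the limit exceeds 8 × ULN from baseline 2.67 and reaches just under 15. Neither tier has a time limit.

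These results are arithmetic on the protocol's own thresholds. They assume that the patient is in the raised-baseline group because of ALT or AST and that the baseline average is the figure multiplied. The documents give no baseline ALT or AST distribution, so the number of patients affected is unknown. Nothing here bears on the validity or power of the efficacy comparison.

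**What to change.** **Recommended.** In both the box and the text of Appendix E, for raised-baseline patients below 2 × ULN, make the stop the lower of >5 × baseline and >8 × ULN, and add a stop at >5 × ULN lasting more than two weeks. Both figures are the protocol's own normal-baseline limits. Leave every existing stop, including the bilirubin/INR and symptom rules, immediate and unchanged.

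**Optional, for the sponsor's hepatologists to decide.** For baselines of 2 to under 5 × ULN, add a separate stop at >10 × ULN, confirmed on the 48-hour repeat test. State explicitly that the >3 × baseline stop remains immediate and needs no confirmation; otherwise the new wording could delay stops that are now automatic. Near baseline 5 this ceiling is only about a 2-fold rise, so it is a matter of clinical judgement. A 5 × ULN duration rule does not suit this tier, because 5 × ULN lies below 2 × baseline once baseline exceeds 2.5.

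**Cost.** The change is to wording only, with no added visits or tests. A few patients would stop study drug sooner. Those who stop before six months have no early-termination biopsy (protocol Section 6.5), count as nonresponders in the ITT analysis (Section 9.2.1.1) and fall outside the SAP's mITT Population (SAP Section 3.2.3). Restart is discretionary: "Reinitiation of study drug may be considered after consultation with the Medical Monitor".

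**What remains.** A step of 2 × ULN stays at baseline 2.0. So does a small duration step: a patient from just under 2.0 must stop after two weeks above 5 × ULN, while one from 2.0 may stay at up to 6. Without the optional ceiling, limits above 8 × ULN remain for baselines of 2.67 to under 5; with it, they run from 8 to 10 × ULN.
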